17.4.2. DEFINITION OF SUSPECTED UNEXPECTED SERIOUS ADVERSE REACTIONS

A Suspected, Unexpected Serious Adverse Reaction (SUSAR) is a subset of SARs that, although foreseeable, are potentially related to the IMP and not identified in the reference safety information. SUSARs will be reported to the appropriate regulatory authorities and Investigators following local and global guidelines and requirements.

17.5. DEFINITION OF SEVERITY OF ADVERSE EVENTS

The term “severe” is used to describe the intensity (severity) of a specific event:

- Mild: causing no limitation of usual activities; the subject may experience slight discomfort;
- Moderate: causing some limitation of usual activities; the subject may experience annoying discomfort;
- Severe: causing inability to carry out usual activities; the subject may experience intolerable discomfort or pain.

17.6. DEFINITION OF ADVERSE EVENT CAUSALITY

Causality shall be determined according to the definition of ADRs as given in [Section 17.3](#).

All AEs judged by either the Investigator or the Sponsor as having a reasonable suspected causal relationship to an IMP qualify as suspected ADRs. The causality assessment given by the Investigator should not be downgraded by the Sponsor.

The following binary decision for causality will be used:

- reasonable possibility that the IMP caused the event;
- no reasonable possibility that the IMP caused the event.

Features supportive of an association include:

- temporal plausibility;
- pharmacological properties of the drug or of the drug substance class;
- course of the AE after dechallenge and, if applicable, after rechallenge;
- specific tests indicating involvement of the drug in the occurrence/worsening of the AE;
- alternative explanations.

17.7. ADVERSE EVENT RECORDING

Each AE occurring to a subject, either spontaneously revealed by the subject or observed by the Investigator, whether believed by the Investigator to be related or unrelated to the IMP, must be recorded by the Investigator on the AE information page of the eCRF. Also, for SAEs, information must be recorded in the eCRF (see [Section 17.8.1](#)).

The Investigator performs an evaluation with respect to seriousness and causality of the AEs and records it on the appropriate section of the eCRF.

17.8. ADVERSE EVENT REPORTING

The Investigator must report to the CRO all AEs which occur during the trial, regardless of their relationship to IMP. All AEs are recorded by the Investigator on the AE information page of the eCRF.

In addition, any SAE will have to be reported according to the following detailed procedure.

17.8.1. REPORTING SERIOUS ADVERSE EVENTS

Investigators must report SAEs **within 24 hours of first becoming aware of the event**.

The SAE must be reported through the eCRF to the CRO's Pharmacovigilance group as given in the contact details provided in the "List of Zambon/CRO personnel" at the beginning of this CTP.

If there is any issue with the electronic reporting process, such as internet failure or database issues, this must not delay SAE reporting. The back-up procedure is to send the back-up paper SAE Form to the CRO's Pharmacovigilance group by email or fax using the following contact details:

Email: CCI [REDACTED]
Fax: CCI [REDACTED]

Note: Any reports submitted on paper must be retrospectively added to the eCRF as soon as possible.

The community standards of confidentiality must always be maintained and any relevant national legislation on data protection must be followed.

SAEs are reportable from the time a subject signs the informed consent to the follow-up phone call 2 weeks after the last dose of IMP.

If the Investigator becomes aware of any SAE occurring to a subject within the follow-up window established in this CTP, he/she will report the SAE as above. The SAE will also be reported in the eCRF.

If the Investigator becomes aware of any SAE outside the follow-up window established in this CTP, it is the Investigator's responsibility to report the SAE to the CRO. The Investigator might use the eCRF, as described above. However, the SAE is not an event which occurred within the trial period.

17.8.2. REPORTING ADVERSE EVENTS OF SPECIAL INTEREST

No specific provisions relate to reporting of AEs of special interest.

17.9. FOLLOW-UP FOR ADVERSE EVENTS

All AEs requiring the subject's discontinuation and SAEs will be followed up until they are resolved or closed.

Resolution of an AE is defined as the return to pre-treatment status or stabilisation of the condition with the expectation that it will remain chronic.

The Investigator must respond to any request for follow-up information (e.g. additional information, outcome and final evaluation, specific records where needed) and answer any question that the Sponsor or designee may have regarding the AE.

Regarding SAEs, the timelines and procedure for follow-up reports are the same as those for the initial reports for SAEs. This is necessary to permit a prompt assessment of the

event by the Sponsor or designee and (as applicable) to allow the Sponsor to meet strict regulatory timelines associated with expedited safety reporting obligations.

If follow-up information on SAEs is available, a follow-up eCRF form will be filled-in by the Investigator and sent to the CRO as described above under [Section 17.8.1](#).

17.10. PREGNANCY

Subjects must be instructed that known or suspected pregnancy occurring during the trial should be confirmed and reported to the Investigator, who must then withdraw the subject from the trial without delay. This also applies in case the partner of a male subject becomes pregnant at any time during the whole course of the study (in this event a specific ICF for the subject's partner will be obtained).

In the event that a subject is subsequently found to be pregnant after inclusion in the trial, then the subject will be withdrawn from the study and the pregnancy will be actively followed up to term and the status of mother and child will be reported by the Investigator to the CRO through the appropriate pregnancy report provided by the CRO.

The Investigator will send pregnancy reports within the timeframes detailed for SAEs.

If pregnancy results in an abnormal outcome that the Investigator and/or the Sponsor considers to be causally related to the IMP, this will be treated as an expedited ADR report.

18. RECORDS

18.1. CASE REPORT FORMS, SOURCE DATA AND QUERY RESOLUTION

The Investigator must ensure that the clinical data required by the CTP are carefully reported in the eCRF. He/she must also check that the data reported in the eCRF correspond to those in the official files (source documentation).

Data entered directly into the eCOA devices for **CCI** assessment are not source data verifiable, though an electronic copy of the subject's **CCI** data must be stored as source data at the investigational site at the end of the trial. If available, spirometry and ECG measurement results must be printed and signed by the Investigator and kept as source data on site after entering details into the eCRF. Adherence data from the **CCI** logging system will not be present at the investigational site as source data as they will be transferred into the eCRF from the sources directly, although copies of the data downloaded should be printed and filed in the subject's notes and will be sent to sites for filing following database lock. The Investigator will receive the results from the central lab by means of a laboratory report, and this should be signed by the Investigator, and stored as source data in the subject's file.

All other data has to be documented in the subject's file as source data first and then entered into the eCRF.

Data must be entered into eCRFs in English by the designated site personnel as soon as possible after a subject visit, and monitors will have access to data recorded. These data will be reviewed versus source documents by trial monitors for completeness and acceptability during monitoring visits. If data correction is required for an eCRF after initial entry, the site personnel can make necessary corrections on their own or as a response to an auto generated query by the eCRF system. The CRA and Clinical Data Manager review

the eCRF for accuracy and can also generate queries to the investigational staff for resolution.

Any correction to the eCRF entries must be carried out by the Investigator or a designated member of staff. Corrections are recorded in an audit trail that records the old information, the new information, and identification of the person making the changes, date of correction made and reason for the change. In the interests of completeness of data acquisition, the questions which are repeated in each section of the eCRFs should be answered in full, even if there are no changes from a previous examination. A reasonable explanation must be given by the Investigator for all missing data. The Investigator or his/her designees named in the clinical staff list will review the eCRF for accuracy and completeness. The Investigator must electronically sign and date the eCRF pages as indicated.

18.2. RECORDS MAINTAINED BY THE INVESTIGATOR

A copy of all trial records (any documents sent or received from the Sponsor/CRO, correspondence with EC/IRB and any other institution or authority and relevant approvals, subjects' source data and subjects' identification documentation) must be maintained by the Investigator for at least 5 years (according to EU directive 2005/28/EC), or for a longer period, where so required by other applicable requirements or by an agreement between the Sponsor and the Investigator. Records will be retained in compliance with applicable FDA and ICH-GCP regulations and guidelines.

18.3. TRIAL MASTER FILE

The Trial Master File (TMF) will be maintained electronically by the CRO according to the respective CRO SOPs with direct access for all relevant Sponsor and CRO personnel.

At the end of the trial, the TMF will be transferred to the Sponsor, where it will be archived according to specific Sponsor SOPs. The Investigator files will be left on site after the end of the study.

18.4. TRIAL MONITORING

The trial will be monitored by means of regular visits and telephone calls according to specific and pre-defined SOPs and trial-specific monitoring guidelines. Details of the visits will be recorded in appropriate Monitoring Report forms to be submitted regularly to the Sponsor. Any relevant protocol deviation must be promptly communicated to designated Sponsor's personnel.

Monitoring will be performed by personnel of the CRO, CCI [REDACTED]. During the Covid-19 pandemic, provisions for remote monitoring and source data verification will be implemented, where possible, in compliance with national and local site procedures and data protection laws.

In addition, to aid data cleaning, a CCI [REDACTED] has been established. The committee is responsible for assessing the impact of Covid-19 on the study and to aid data cleaning by conducting a blinded review of the primary efficacy endpoint variable, to ensure the protocol-defined pulmonary exacerbations have been appropriately recorded and proposing data queries for Investigators to respond to, where appropriate. The CCI [REDACTED] only ask questions of the Investigators and do not change any data entered by sites.

18.5. CONFIDENTIALITY OF SUBJECT'S INFORMATION

The Investigator has the responsibility to maintain the anonymity of subjects in compliance with the Italian data protection law. In all trial documents, subjects are associated to a code which does not reveal the subject's identity. Only at the site, the Investigator holds the subject's identity on a Subject Identification Log under his/her responsibility. The Investigator will maintain this for the longest period allowed by his/her own institution and, in any case, until further communication from the Sponsor.

The site and the Sponsor shall process personal data of subjects involved in the clinical trial as data controllers and in compliance with the Italian data protection law, each of them in its area of competence and in accordance with the responsibilities provided by GCP, only in relation to the trial performance and for pharmacovigilance purposes.

Any contracted organisation as data processor including Syneos Health, the central laboratory, eCOA provider, and IWRS provider, will act in compliance with the terms and conditions agreed with the Sponsor. All data will be handled in compliance with Regulation (EU) 2016/679 of the European Parliament and of the Council on the protection of natural persons with regard to the processing of personal data.

19. BIOMETRICS

19.1. DATA MANAGEMENT

A data management plan specifying all relevant aspects of data processing for the study (including data validation, cleaning, correcting, and releasing) will be maintained and stored at Syneos Health.

Electronic systems that may be used to process and/or collect data in this study will include the following:

- IWRS system – randomisation, study drug supply
- Electronic Data Capture system – eCRFs
- eCOA device - **CCI** data capture
- Statistical Analysis System (SAS®) – statistical review and analysis
- Pharmacovigilance safety database

Subject data will be captured in an eCRF system and reviewed by the CRA in order to check CTP adherence and to detect any data inconsistency or discrepancy (data validation step).

Medical/surgical history and underlying diseases and AEs will be coded using the Medical Dictionary for Regulatory Activities (MedDRA) latest version current at trial start and which will be maintained during the trial.

Previous and concomitant medications will be coded using the World Health Organization-Drug Dictionary (WHO-DD). Actual versions of coding dictionaries used will be stated in the Clinical Trial Report (CTR).

The final data file will be transferred to the Sponsor in the agreed format as soon as possible after the trial is completed.

19.2. STUDY VARIABLES

Primary Efficacy Variable

The primary variable for this trial is the mean annual NCFB pulmonary exacerbation rate.

Secondary Efficacy Variables

- CCI [REDACTED]
- [REDACTED]
- [REDACTED]
- [REDACTED]
- [REDACTED]
- [REDACTED]
- [REDACTED]

Safety Variables

- the incidence of TEAEs;
- absolute changes in percent-predicted FEV₁ from baseline (Visit 2) to each post-baseline visit;
- the number of subjects experiencing bronchospasm clinically or spirometrically determined following IMP administration at the start and end of treatment;
- CCI [REDACTED] from Screening/Randomisation (Visit 1/Visit 2) to Visits 3, 5 and end of treatment (Visit 7) as well as on CCI [REDACTED] from Exacerbation Visits and clinic visits due to pneumonia;
- emergence of other bacterial colonies and any developing resistance in CCI [REDACTED] from Screening (Visit 1) to End of Treatment (Visit 7);
- haematology, clinical chemistry and renal function tests;
- physical examination and vital signs data;
- 12-lead electrocardiogram.

19.3. SAMPLE SIZE

The sample size has been calculated considering the results from the previous trial (CCI [REDACTED]), relevant literature and the clinically meaningful benefit the treatment should provide. A treatment difference of CCI [REDACTED] between the colistimethate sodium and placebo groups CCI [REDACTED].

For the purpose of the power calculation, a simulation of exacerbations has been carried out by randomly assigning a patient a value from the gamma distribution according to the treatment group they are in and then generating a CCI [REDACTED] event rate using this parameter. This CCI [REDACTED] leads to two negative binomials with the following parameter values:

CCI [REDACTED]

CCI

These are rates per year. Note that, since the variances are greater than the mean, this means that there is mild over-dispersion.

Under these assumptions, a CCI allowing for over-dispersion for frequency of exacerbation (FOE), with a two-sided significance level of 0.05, a treatment effect of CCI and a follow-up time of CCI, assuming a frequency of CCI pulmonary exacerbations per annum for the FOE, a sample size of 170 completed subjects per group will provide a power of CCI

Assuming a drop-out rate of about CCI, the total sample size should be approximately 210 subjects per treatment group (420 total subjects). It is anticipated that a blinded review of the exacerbation rate across treatment groups will be conducted prior to database lock to determine whether the FOE is in line with the assumptions above, given the potential impact of Covid-19. The sample size will then be recalculated and, in addition, take into consideration treatment exposure for withdrawn subjects at that stage.

19.4. STATISTICAL ANALYSES

The statistical analysis will be performed by the CRO and it will be carried out according to ICH guidelines ICH E9: “Statistical Principles for Clinical Trials” (CPMP/ICH/363/96 September 1998) and ICH E10 “Choice of Control Group in Clinical Trials” (CPMP/ICH/364/96 January 2001).

All the statistical analyses and outputs will be produced using SAS release 9.2 or later (SAS Institute, Inc. Cary, NC, USA).

The data from all countries and all sites will be pooled and summarised. Unless stated otherwise, all available data from withdrawn subjects will be included in the analysis up to the time of withdrawal.

Descriptive statistics will be used to present all efficacy and safety results: number of observations, mean, standard deviation, median, minimum, maximum for continuous data and frequency and percentage for categorical data. Statistics will be displayed by treatment group.

The analysis of the trial is on a comparative basis. Two-sided p-values <0.05 will be considered statistically significant and 95% two-sided confidence intervals (CIs) will be presented, where appropriate. Any adjustment for multiplicity will be detailed in the Statistical Analysis Plan (SAP).

More details about the statistical analysis will be provided in the SAP. The plan might be reviewed and updated as a result of the blind review of the data and will be finalised before breaking the blind. Any deviations from the SAP which occurred after breaking the blind will be documented and justified in the final CTR and deviations will be clearly marked as ‘post hoc’ analysis.

19.4.1. TRIAL POPULATIONS

There will be 4 analysis populations defined for the trial analyses:

Intention-To-Treat (ITT) Population

The Intention-To-Treat Population will include all subjects who provided informed consent and received a patient number (randomisation number) whether or not they receive IMP.

Modified Intention-To-Treat Population

The Modified ITT (mITT) Population will comprise all subjects who provided informed consent, were randomised and received at least 1 dose or partial dose of the IMP. Primary analyses will be performed on the mITT population with exclusions from the ITT defined and justified in the SAP.

Following the ITT principle, subjects will be analysed according to the treatment they have been assigned to at randomisation.

The mITT will be used to produce summaries of baseline subject characteristics and for the analysis of all efficacy variables.

Safety Population

The Safety Population will comprise all subjects who provide Informed Consent and received at least 1 dose or partial dose of IMP.

Subjects will be analysed according to the treatment they actually received.

The Safety Population will be used to produce summaries of all safety-related variables and demography.

Per-Protocol Population

The Per-Protocol Population (PP) will include all mITT subjects who were compliant with study drug administration (i.e. had a compliance of at least 80%) and who had no major protocol deviations that were considered as potentially impacting the efficacy results. Major protocol deviations might include, but are not limited to, subjects taking a non-permitted concomitant medication, the IMP not being administered during the trial as defined in the protocol, subjects receiving a treatment different than the one assigned by randomisation; others will be defined in the SAP.

Results of the primary and secondary efficacy analyses conducted in the PP will be considered as supportive.

Exclusion of subjects from the PP analyses will be decided jointly by the CRO and Sponsor's Medical Monitor, Clinical Trial Manager and Statistician prior to unblinding of the randomisation code and database release.

The subjects or observations to be excluded, and the reasons for their exclusion will be documented and approved by the above-mentioned persons prior to database release. The documentation will be filed together with the remaining trial documentation.

The number of subjects in each analysis population will be reported. Violations excluding subjects from any particular population will be described, reporting the number of protocol violators for each criterion. All protocol violations, minor ones included, will be listed.

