3.5.2 Modified Intention-To-Treat Population

The modified ITT (mITT) Population will comprise all subjects who provided informed consent, were randomised and received at least 1 dose or partial dose of the IMP.

Subjects will be analysed according to the treatment they have been assigned to at randomisation.

The mITT will be used to produce summaries of baseline subject characteristics and for the analysis of all primary and secondary efficacy endpoints. Minimal difference in sample size is expected between ITT and mITT. Being a double-blind study, no bias due to the exclusion of the non-treated subjects is expected. Exposure variables will also be presented for the mITT.

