3.5.3 Safety Population

The Safety Population will comprise all subjects who provided informed consent, were randomised and received at least 1 dose or partial dose of IMP.

Subjects will be analysed according to the treatment they actually received.

The Safety Population will be used to produce summaries of all safety related endpoints and demography.

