4.1.1 Populations for the Analysis

Demographics and baseline characteristics will be summarised for the mITT population. Demographics and selected baseline characteristics will be also presented for the Safety Population.

The following baseline characteristics will be presented on the mITT Population only:

- Smoking and Alcohol Status
- Non-CF Bronchiectasis History
- Past and Concomitant Relevant Diseases, Diagnosis or Surgeries
- Prior and Concomitant Medication.

No baseline testing will be performed.

Primary and relevant secondary efficacy variables will be summarised and analysed for the mITT and PP Population. Results on PP will be considered as supportive. CCI will only be done on the mITT population.

The number of days of work absence and hospitalisations will be analysed for the mITT population only.

The exposure data will be analysed on the Safety and mITT Populations.

The safety variables will be summarised for the Safety Population.

In case an error occurs in treatment allocation, the following rules will be followed:

- If a subject was randomised but received the incorrect treatment for all the time the subject was in the study, he/she will be reported under the randomised treatment group for all analyses performed on the ITT and on the mITT Population (and in listings on all screened subjects). He/she will be reported under the treatment actually received for all analyses performed on the Safety Population (i.e. an as-treated analysis will be performed). Such subjects will be excluded from the PP Population.
- If a subject received the incorrect treatment after being treated with the correct one, it's foreseen that the subject will be withdrawn from the study. Data for this subject will be

CONFIDENTIAL

Sponsor:	Zambon S.p.A.	Protocol Number:	Z7224L02
----------	---------------	------------------	----------

analysed until the date of the wrong treatment dispensing. All the data collected after that date will be reported in listings and flagged, but not included in the summary statistics. He/she will be reported under the randomised treatment group for all analyses performed and listings presented.

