4.8 Safety Analysis

All safety variables will be summarised overall and by treatment group using the Safety Population.

The safety variables are:

- AEs;
- Spirometry results;
- CCI [REDACTED] CCI [REDACTED]
- Vital signs;
- Physical examination results;
- Haematology and clinical chemistry parameters;
- 12-lead ECG parameters.

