4.10 Protocol Deviations

4.10.1 Major Protocol Deviation Criteria

Exact definitions of major protocol deviations affecting safety and efficacy analyses will be discussed at the blind review meeting and documented in the Blind Data Review and Analysis Sets Report. The Protocol Deviation and Non-Compliance Management Plan documents the process for identifying protocol deviations that would potentially exclude subjects from the PP Population.

If major protocol deviations occur as outlined in the criteria below, then the data from complete individual subjects, individual visits or individual evaluations will be excluded from the population of analysis as indicated.

Exclusion of subjects or observations from the analyses will be decided jointly by the CRO and Sponsor’s Study Team prior to unblinding of the randomisation code and database release.

The subjects or observations to be excluded, and the reasons for their exclusion, will be documented and approved by the above-mentioned persons prior to database release. The documentation will be filed together with the remaining trial documentation.

The number of subjects in each analysis population will be reported. Major protocol deviations excluding subjects from any particular population will be described, reporting the number of protocol violators for each criterion. All major protocol deviations will be listed and summarised for all screened subjects.

Major protocol deviations will be classified according to the following categories:

- Concomitant Medication / Administration of Prohibited Medication;
- Inclusion or Exclusion Criteria;
- Informed Consent / ICF not signed or signed late;
- Informed Consent / Other;
- Investigational Product / Incorrect IMP kit given to subject;
- Investigational Product / IMP Dosing;
- Investigational Product / IMP Storage;

CONFIDENTIAL

Sponsor:	Zambon S.p.A.	Protocol Number:	Z7224L02
----------	---------------	------------------	----------

- Investigational Product / Other;
- Met Withdrawal Criteria but was not Withdrawn;
- Patient Privacy (PP) / PP not signed;
- Patient Privacy / Other;
- Randomization / Mis-stratification;
- Randomization / Multiple Randomizations;
- Randomization / Other;
- Randomization / Randomized Not Treated;
- Randomization / Treated and Not Randomized;
- SAE not reported or reported late;
- Study Procedure / Missed procedure;
- Study Procedure / Other;
- Study Procedure / Site Staff Authorization, Delegation, Training;

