4.13 Changes in Conduct or Planned Analyses from the Protocol

Sections 2.2, 4.4.11, 4.7.5 and 4.7.6.3: The protocol incorrectly referred to the units for the determination of CCI CCI which have been reported as CCI by the central laboratory.

Section 4.7.4: The protocol states that the Negative Binomial Model will consider the log-time on study as offset. However, as specified in Section 4.1.7, NCFB Pulmonary Exacerbations analyses focus on the treatment period so log-time on treatment will be considered.

Sections 4.7.5 and 4.7.6.1: The protocol states that the CCI
[REDACTED]
[REDACTED]. Using date of first IMP as the start time of risk is considered to be biased, so date of randomisation will be used instead.

CONFIDENTIAL

Sponsor:	Zambon S.p.A.	Protocol Number:	Z7224L02
----------	---------------	------------------	----------

Section 4.7.6.1: The protocol states that the CCI [REDACTED] CCI [REDACTED] For time-to-event endpoints, generally the + 1 is not included because this overestimates the time by 1 day for every event, therefore “+ 1” has been deleted.

Section 4.7.6.5: The protocol states that the CCI [REDACTED] total score will be computed and analysed. However, as recommended in the Manual Scoring Instructions [REDACTED], only the CCI [REDACTED] domain scores will be presented and analysed.

There have been no other changes in analyses from those defined in the protocol.

CONFIDENTIAL

Sponsor:	Zambon S.p.A.	Protocol Number:	Z7224L02
----------	---------------	------------------	----------

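### SAP 3.5.3 adds randomisation to the protocol's Safety Population definition without declaring it, so a subject dosed but not randomised would be left out of the Safety Population summary tables

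*Protocol*

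**What the plan says.** Protocol 19.4.1 sets two conditions for the Safety Population, consent and exposure: "The Safety Population will comprise all subjects who provide Informed Consent and received at least 1 dose or partial dose of IMP". Subjects are analysed by the treatment they actually received. The same section does require randomisation for the mITT population.

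SAP 3.5.3 keeps the as-treated grouping but sets three conditions: "The Safety Population will comprise all subjects who provided informed consent, were randomised and received at least 1 dose or partial dose of IMP". The SAP's mITT definition (3.5.2) has the same three: consent, and subjects who "were randomised and received at least 1 dose or partial dose of the IMP".

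Four other places in the SAP bear on the point:

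- Section 4.8 ties the safety analysis to this set: "All safety variables will be summarised overall and by treatment group using the Safety Population".
- Section 4.10.1 includes "Randomization / Treated and Not Randomized" among its major deviation categories.
- Section 4.1.1 gives rules for treatment-allocation errors. The first begins "If a subject was randomised but received the incorrect treatment for all the time the subject was in the study". The second covers a subject who moves from the correct to an incorrect treatment and reports that subject under the randomised group.
- Section 4.13 lists changes from the protocol and closes with "There have been no other changes in analyses from those defined in the protocol". The Safety Population is not on the list.

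**The concern.** A safety set is meant to hold everyone exposed to the product, because harm follows from exposure and not from the act of randomisation. The protocol's definition does that, and it looks deliberate: within one section, randomisation is a condition for mITT and is absent for Safety. The SAP removes the distinction, so its Safety and mITT sets have the same members and differ only in whether subjects are grouped as treated or as randomised.

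Two things are at stake. The first is an exposed subject whose adverse events, spirometry, laboratory values, vital signs and ECG would be missing from the safety summaries. For rare outcomes, such as related serious events, one subject can change a table. The second is accuracy: 4.13 tells the reader that nothing else was changed, and for this definition that is not so, whether or not any subject is affected.

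**Working it through.** No figure in the plan needs reproducing. The check sets the definitions side by side and follows one subject through them.

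**Membership conditions**

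| Set | Consent | Randomised | At least one full or partial dose |
|---|---|---|---|
| Protocol 19.4.1, Safety | required | not required | required |
| SAP 3.5.3, Safety | required | required | required |
| SAP 3.5.2, mITT | required | required | required |
| SAP 3.5.1, ITT | required | required (randomisation number) | not required |

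The SAP's Per-Protocol set (3.5.4) is a subset of mITT.

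**A subject who consented, was dosed and was not randomised**

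- Protocol Safety Population: included.
- SAP Safety, mITT, ITT and Per-Protocol: excluded from all four.
- SAP 4.1.1 error rules: neither applies. The first is limited to randomised subjects. The second presupposes a correct, randomised treatment. Nothing brings the subject back.

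**Where the subject would be missing.** The summary tables in SAP 5.3.4 numbered 14.3.1.x (adverse events) and 14.3.4.x (spirometry, vital signs, physical examination, ECG, laboratory, and the last pair by previous colistin use) all carry the Safety Population label. So do the Safety versions of the demography and exposure tables in 5.3.1 (14.1.4.2, 14.1.10.1, 14.1.11.1 and 14.1.13.1).

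**Where the subject would still appear.** Tables 14.3.2.1 to 14.3.2.3 (deaths, serious events, events leading to discontinuation) are listings with no population named. SAP 4.1.12 has all collected data listed. SAP 4.10.1 has all major deviations listed and summarised for all screened subjects.

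**Size.** Let *k* be the number of subjects dosed but not randomised.

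- Protocol Safety set = (randomised and dosed) + *k*
- SAP Safety set = (randomised and dosed)
- Difference = *k*

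The documents do not give *k*. SAP 3.9 states that 287 subjects had been randomised when recruitment stopped. By definition none of the *k* is among those 287, so *k* cannot be expressed as a share of them. If *k* = 0, no table changes. If *k* = 1, every Safety Population denominator is one short and that subject's events are absent from the counts.

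**How likely *k* > 0 is.** Protocol 9.2 has randomisation and kit assignment in the same IWRS step, with the first dose supervised at that visit. Protocol 12.1 manages IMP allocation through the IWRS, and 12.4 records there what was dispensed to whom. A dose outside randomisation would need a failure of that chain.

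**The case against.** The strongest reply is that the added words change nobody's membership in practice. Under the protocol's procedures a subject receives a kit only by being randomised, so dosed ordinarily implies randomised. The deviation category comes from a broad list that also covers storage, privacy and staff delegation, and that the SAP says may be amended. Any exclusion would also be visible: SAP 4.10.1 requires population counts, the exclusions by criterion, and documented decisions before unblinding.

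Most of this stands, and it limits the point. A reader might infer from the category that the sponsor expected or knew of such cases. A classification heading does not show that, and no document reports a case. A reader might also infer that the subject's safety data would vanish from the report. They would not, because the listings, including those for deaths and serious events, are not restricted to the Safety Population.

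What the reply does not do is reconcile the two definitions. If the words change nobody's membership, they are not needed. If they do change it, they remove exactly the subject the protocol meant to keep. Discussion at the blind review meeting may bring a case to light, but the SAP gives it no rule to apply, and visibility does not correct the closing statement of 4.13.

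**Conclusion.** The point holds as an undeclared conflict between protocol and SAP with a small expected effect. That the definitions differ, that the difference is not declared in 4.13, and that a dosed, unrandomised subject falls outside the SAP's Safety Population all follow directly from the text.

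The numerical consequence is conditional. It is limited to the summary tables labelled Safety Population and equals the number of such subjects, which is unknown and probably very small or zero given the IWRS control of kits. A reader might be tempted to conclude that the trial's safety results are distorted. The documents do not support that, since they give no evidence of even one case. Efficacy conclusions are untouched, because mITT requires randomisation in both documents.

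**What to change.** 1. In SAP 3.5.3, delete *were randomised* so that the definition matches protocol 19.4.1. Keep randomisation as a condition for ITT and mITT.
2. In SAP 4.1.1, add a rule: a subject treated but not randomised is grouped in the safety analyses by the product actually received, traced through the IMP accountability records (protocol 12.4). If the product cannot be traced, the subject is counted only in the Overall column that SAP 4.1.2 and 4.8 already provide.

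If the sponsor prefers the narrower set, it should be declared and justified in 4.13, with the number of exposed subjects it excludes. If the SAP can no longer be amended, the clinical trial report should state the difference and that number, even if it is zero.

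The cost is two deleted words and one added grouping rule. No efficacy analysis changes. Safety output changes only if such a subject exists.
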